8.5.3. Plasma for Analysis of Unlabeled PF-06865571 (Periods 1 and 2)

During **Periods 1 and 2**, blood samples of approximately 3 mL to provide approximately 1.2 mL of plasma for PK analysis of unlabeled PF-06865571 will be collected into appropriately labeled tubes containing K₂EDTA at times specified in the [Schedule of Activities](#).

Instructions for the collection and handling of biological samples will be provided in the laboratory manual or by the sponsor. The actual date and time (24-hour clock time) of each sample will be recorded.

The actual times may change, but the number of samples will remain the same. All efforts will be made to obtain the samples at the exact nominal time relative to dosing. Collection of samples up to and including 10 hours after dose administration that are obtained within 10% of the nominal time relative to dosing (eg, within 6 minutes of a 60-minute sample) will not be captured as a protocol deviation, as long as the exact time of the collection is noted on the source document and the CRF. Collection of samples more than 10 hours after dose administration that are obtained \leq 1 hour away from the nominal time relative to dosing will not be captured as a protocol deviation, as long as the exact time of the collection is noted on the source document and the CRF. This protocol deviation window does not apply to samples to be collected more than 10 hours after dose administration at outpatient/follow-up visits with visit windows.

Details regarding the collection, processing, storage and shipping of the blood samples will be provided in the lab manual.

Samples collected for measurement of plasma concentrations of PF-06865571 will be analyzed using a validated analytical method in compliance with applicable SOPs.

8.5.4. Urine for Analysis of Total ¹⁴C (Oral and IV) and Metabolite Profiling/ID

Urine will be collected for determination of total ¹⁴C measurement and metabolite profiling/ID following oral administration of [¹⁴C]PF-06865571 (**Period 1** only) and for determination of total ¹⁴C measurement following IV administration of [¹⁴C]PF-06865571 (**Period 2** only), at predose and at post dose intervals as specified in the [Schedule of Activities](#).

Each participant will empty his bladder just prior to dosing on Day 1 and an aliquot from this collection will be used as “urine blank”. During the entire collection period, the urine collection container should be refrigerated. At the end of each urine collection period, the total volume will be measured and recorded. All urine aliquots should be collected using a new pipette tube for each participant at each time interval. All urine samples within each collection interval will be mixed thoroughly before aliquoting.

Details regarding the collection volume, processing, storage and shipping of the urine samples will be provided in the lab manual.

8.5.5. Feces for Analysis of Total ^{14}C (Oral and IV) and Metabolite Profiling/ID

Feces will be collected for determination of total ^{14}C measurement and metabolite profiling/ID following oral administration of [^{14}C]PF-06865571 in **Period 1** at times specified in the [Schedule of Activities](#). Feces will be collected following IV administration of [^{14}C]PF-06865571 in **Period 2** at times specified in the [Schedule of Activities](#), and may be analyzed for total ^{14}C and/or [^{14}C]PF-06865571 determination and/or metabolic profiling/ID if the fraction of dose excreted as parent in feces of Period 1 is 0.25 greater than unabsorbed drug (1-Fa), indicating biliary and/or GI excretion may be a major pathway for parent drug clearance (e.g. greater than 25% of total clearance).

Fecal voids will be collected at the clinic and immediately frozen. The sample will be labeled and frozen at approximately -20°C.

Total fecal mass is to be recorded for each 24-hour period. Each bowel movement must be collected. Time and date must be recorded.

In the event of diarrhea during the study, all diarrhea, including any swabbing and contaminated linen, should be collected, labeled, and stored in appropriate containers at -20°C for possible analysis of radioactivity. Following completion of radioanalysis and subsample collections for metabolite profiling/ID, the remaining bulk fecal homogenate will be discarded upon approval from the sponsor.

Details regarding the collection, processing, storage and shipping of the feces samples will be provided in the lab manual.

All feces samples must be processed and shipped as indicated to maintain sample integrity. Any deviations from the processing steps, including any actions taken, must be documented and reported to the sponsor. On a case-by-case basis, the sponsor may make a determination as to whether sample integrity has been compromised. Any sample deemed outside of established stability, or of questionable integrity, will be considered a protocol deviation.

8.5.6. Emesis

If emesis occurs within 24 hours after oral administration of [^{14}C]PF-06865571 (**Period 1** only), then the vomitus must be collected and stored for a radioactivity assessment. All emesis including any swabbing, contaminated linens and facial tissues used to collect bodily discharge; eg, nose bleeding clean-up tissue and any emesis related clean-up is to be collected and stored at -20°C for possible analysis of radioactivity.

Details regarding the collection, processing, storage and shipping of the samples will be provided in the lab manual.

8.6. Pharmacodynamics

Pharmacodynamic parameters are not evaluated in this study.

8.7. Genetics

8.7.1. Specified Genetics

Genetics (specified analyses) are not evaluated in this study. Any genetic analysis, if conducted, will not be part of this study report.

8.7.2. Banked Biospecimens for Genetics

A 2 mL blood sample optimized for DNA isolation Prep D1.5 will be collected as local regulations and IRBs/ECs allow.

Banked Biospecimens may be used for research related to the study intervention(s) and/or NAFLD/NASH. Genes and other analytes (eg, proteins, RNA, nondrug metabolites) may be studied using the banked samples.

See [Appendix 5](#) for information regarding genetic research. Details on processes for collection and shipment of these samples can be found in supporting documentation.

8.8. Biomarkers

Collection of samples for biomarker research is also part of this study.

The following sample for biomarker research are required and will be collected from all participants in this study as specified in the [Schedule of Activities](#):

- Whole blood (Prep B1) Banked Biospecimen optimized for plasma

8.8.1. Specified Gene Expression (RNA) Research

Specified gene expression (RNA) research is not included in this study.

8.8.2. Specified Protein Research

Specified protein research is not included in this study.

8.8.3. Specified Metabolomic Research

Specified metabolomic research is not included in this study.

8.8.4. Banked Biospecimens for Biomarkers

Additional Banked Biospecimens in this study are:

- 10 mL whole blood Prep B1 optimized for plasma

Banked Biospecimens will be collected as local regulations and IRB/ECs allow.

Banked Biospecimens may be used for research related to the study intervention(s) and NAFLD/NASH. Genes and other analytes (eg, proteins, RNA, nondrug metabolites) may be studied using the banked samples.

See [Appendix 5](#) for information regarding genetic research. Details on processes for collection and shipment of these samples can be found in supporting documentation.

8.9. Immunogenicity Assessments

Immunogenicity assessments are not included in this study.

8.10. Health Economics

Health economics/medical resource utilization and health economics parameters are not evaluated in this study.

CCI

9. STATISTICAL CONSIDERATIONS

Detailed methodology for summary and statistical analyses of the data collected in this study is outlined here and further detailed in a SAP, which will be maintained by the sponsor. The SAP may modify what is outlined in the protocol where appropriate; however, any major modifications of the primary endpoint definitions or their analyses will also be reflected in a protocol amendment.

9.1. Statistical Hypotheses

No statistical hypothesis is tested in this study.

9.2. Sample Size Determination

A sample size of 6 male participants has been chosen based on the industry standard sample size for ADME Mass Balance studies and radiolabeled tracer studies. This sample size was not chosen based on any empirical data or hypothesis testing criteria.

Participants who withdraw from the study, for non-safety reasons, may be replaced if the number of participants with evaluable data is less than 4.

9.3. Analysis Sets

For purposes of analysis, the following analysis sets are defined:

Participant Analysis Set	Description
Evaluable	All participants assigned to study intervention and who take at least 1 dose of study intervention.

Participant Analysis Set	Description
Extent of Excretion	Extent of excretion population is defined as all participants who have received 1 dose of [¹⁴ C]PF-06865571 and who have evaluable total radioactivity concentration (urinary and fecal) data and who had no protocol deviations or AEs (such as vomiting of the dose, diarrhoea or severe constipation) that may have affected the extent of excretion analysis.
PK Concentration	The PK concentration population for PF-06895571 is defined as all participants who receive at least 1 dose of PF-06895571 and who have at least 1 measurable concentration of PF-06895571. The PK concentration population for ¹⁴ C is defined as all participants dosed with [¹⁴ C]PF-06895571, who have at least one ¹⁴ C measurement.
PK Parameter	The PK parameter analysis population for PF-06895571 is defined as all participants treated who have at least 1 of the PF-06895571 PK parameters of interest. The PK parameter analysis population for ¹⁴ C analysis is defined as all participants treated who have at least one of the ¹⁴ C parameters of interest. The PK concentration and PK parameter analysis sets may differ.
Safety	All participants assigned to study intervention and who take at least 1 dose of study intervention. Participants will be analyzed according to the product they actually received.

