Total Radioactivity ^q (P2 Only)							X	→	→	→	→	→	→	→	→	→	X	→	→	X	→	→	X ^q				
Feces Sample collection for -																											
Total Radioactivity and Metabolite ID ^r (P1 Only)		X ^r	X	→	→	→	→	→	→	→	→	→	→	→	→	→	→	X	→	→	X	→	X	X	X	X ^r	X
[¹⁴ C]PF-06865571 ^r (P2 Only)							X ^r	→	→	→	→	→	→	→	→	→	→	→	→	→	→	X	→	→	X ^r		

Abbreviations: →= ongoing/continuous event; AE = adverse event; COVID-19 = Coronavirus disease 2019; CRU = Clinical Research Unit; ECG = electrocardiogram; ET=early termination; F/U=follow-up; HCVAb = hepatitis C antibody; HBsAg = hepatitis B surface antigen; HIV = human immunodeficiency virus; P1 = Period 1; P2 = Period 2; PK = pharmacokinetics; SAE = serious adverse event; LC/MS = liquid chromatography tandem mass spectrometry; ET = early termination.

Visit Identifier	Screening	Period 1 (P1) and Period 2 (P2), unless otherwise limited to 1 of these 2 Periods ^a																					F/U Phone Call	ET	
Days Relative to Day 1	-42 to -2	-1																							
Hours After Oral PF-06865571 Dose	-	-	0	0.5	1	2	3	3.08	3.17	3.25	3.5	3.75	4	6	9	12	16	24	27	36	48	51	72	96	120
Hours After IV [¹⁴ C]PF-06865571 Dose (P2 Only)			-3				0	0.08 3 (5 min)	0.17 (10 min)	0.25 (15 min)	0.5 (30 min)	0.75 (45 min)	1	3	6	9	13	21	24	33	45	48			

Note: Black color denotes oral dose administration and sampling post oral administration and Red color denotes IV dose administration and sampling post IV administration. IV samples may optionally be labeled with the corresponding time relative to the oral dose for sample collection; however, PK data for the IV administration will be analyzed relative to the start of the IV infusion.

- There will be a wash-out period of 8-22 days from drug administration in Period 1 and Period 2. The day to start Period 2 is dependent on the duration for Period 1 but will be at least after all sample collection in Period 1 are complete.
- In Period 2, participants will be discharged on Day 3 (ie, 48 hours IV dose administration).
- Dosing in Period 2 (as 1 cohort) or Completion of Period 1 (1 participant at a time) when at least 1 of 3 criteria are met: (1) ≥90% of radioactive dose has been recovered in urine+feces+emesis (if any); (2) <1% of radioactive dose has been recovered in urine+feces during 24H interval over 2 consecutive days; (3) participant has reached Day 21 (in Period 1). At the latest, Period 2, Day -1 would occur on the same day as Period 1, Day 21.

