4. STUDY DESIGN

4.1. Overall Design

This study is a Phase 1, open-label, non-randomized, 2-period, fixed-sequence, single-dose study of PF-06865571 in healthy male participants to characterize the ADME properties of [¹⁴C]PF-06865571 following oral administration; and to evaluate the absolute oral bioavailability (F) and fraction absorbed (Fa) of PF-06865571 following oral administration of unlabeled PF-06865571 and IV administration of [¹⁴C]PF-06865571.

In this study 6 participants will be enrolled to ensure evaluable data is acquired in at least 4 participants. Each participant will receive 2 regimens (A and B) in Periods 1 and 2, respectively, as outlined in Figure 1. Participants who withdraw from the study may be replaced if the number of evaluable participants is less than 4.

Figure 1. Two (2)-Period Fixed Sequence Study Design

* Completion of Period 1 (1 participant at a time) when at least 1 of 3 criteria are met: (1) $\geq 90\%$ of radioactive dose has been recovered in urine+feces+emesis (if any); (2) $< 1\%$ of radioactive dose has been recovered in urine+feces during 24H interval over 2 consecutive days; (3) participant has reached Day 21 (in Period 1). At the latest, Period 2, Day -1 would occur on the same day as Period 1, Day 21.

Regimen A in Period 1: An oral dose of 300 mg PF-06865571 containing approximately 300 nCi ^{14}C (ie, radiolabeled PF-06865571) will be administered within approximately 10 minutes of completion of a standard breakfast (see Sections 5.3.1 and 6.1.1).

Regimen B in Period 2: An oral dose of 300 mg unlabeled PF-06865571 followed at T_{max} by an IV dose of 300 nCi $[^{14}\text{C}]$ in 100 μg of PF-06865571 (3 $\mu\text{Ci}/\text{mg}$ active drug). The $[^{14}\text{C}]$ IV dose will be administered as an infusion over approximately 15 minutes. Oral unlabeled PF-06865571 will be administered within approximately 10 minutes of completion of a standard breakfast (see Sections 5.3.1 and 6.1.1).

Screening will occur within 42 days of the first dose of the investigational product in Period 1. All participants will provide informed consent and undergo screening evaluations to determine their eligibility.

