7. DISCONTINUATION OF STUDY INTERVENTION AND PARTICIPANT DISCONTINUATION/WITHDRAWAL

7.1. Discontinuation of Study Intervention

In rare instances, it may be necessary for a participant to permanently discontinue study intervention (definitive discontinuation). Reasons for definitive discontinuation of study intervention include the following: intolerance of the study drug, SAE, clinically relevant laboratory, vital signs or ECG changes.

If study intervention is definitively discontinued, the participant will not remain in the study for further evaluation. See the [Schedule of Activities](#) for data to be collected at the time of discontinuation of study intervention.

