7.2.1. Withdrawal of Consent

Participants who request to discontinue receipt of study intervention will remain in the study and must continue to be followed for protocol-specified follow-up procedures. The only exception to this is when a participant specifically withdraws consent for any further contact with him or her or persons previously authorized by the participant to provide this information. Participants should notify the investigator in writing of the decision to withdraw consent from future follow-up, whenever possible. The withdrawal of consent should be explained in detail in the medical records by the investigator, as to whether the withdrawal is only from further receipt of study intervention or also from study procedures and/or posttreatment study follow-up, and entered on the appropriate CRF page. In the event that vital status (whether the participant is alive or dead) is being measured, publicly

available information should be used to determine vital status only as appropriately directed in accordance with local law.

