2.1. Study Design

This study is a Phase 1, open-label, non-randomized, 2-period, fixed-sequence, single-dose study of PF-06865571 in healthy male participants to characterize the ADME properties of $[^{14}\text{C}]$ PF-06865571 following oral administration; and to evaluate the absolute oral bioavailability (F) and fraction absorbed (Fa) of PF-06865571 following oral administration of unlabeled PF-06865571 and IV administration of $[^{14}\text{C}]$ PF-06865571.

In this study, 6 participants will be enrolled to ensure evaluable data is acquired in at least 4 participants. Each participant will receive 2 regimens (A and B) in Periods 1 and 2, respectively, as outlined in Figure 1. Participants who withdraw from the study may be replaced if the number of evaluable participants is less than 4.

Figure 1. Two Period Fixed Sequence Study Design

* Completion of Period 1 (1 participant at a time) when at least 1 of 3 criteria are met: (1) $\geq 90\%$ of radioactive dose has been recovered in urine+feces+emesis (if any); (2) $< 1\%$ of radioactive dose has been recovered in urine+feces during 24H interval over 2 consecutive days; (3) participant has reached Day 21 (in Period 1). At the latest, Period 2, Day -1 would occur on the same day as Period 1, Day 21.

Regimen A in Period 1: An oral dose of 300 mg PF-06865571 containing approximately 300 nCi ^{14}C (ie, radiolabeled PF-06865571).

Regimen B in Period 2: An oral dose of 300 mg unlabeled PF-06865571 followed at T_{max} by an IV dose of 300 nCi $[^{14}\text{C}]$ in 100 μg of PF-06865571 (3 $\mu\text{Ci}/\text{mg}$ active drug).

Screening will occur within 42 days of the first dose of the investigational product in Period 1. All participants will provide informed consent and undergo screening evaluations to determine their eligibility.

Eligible participants will be admitted to the CRU on Day -1 of Period 1 and scheduled to remain in the CRU through the completion of Period 2. As such, inpatient stay will be for a total duration of 12 days (minimum) to 25 days (maximum). Each participant will have 1 follow-up phone call that will occur at least 28 days and up to 35 days following the last dose of investigational product to assess for AEs and SAEs.

A participant is considered to have completed the study if he has completed all phases of the study, including the last scheduled procedure as mentioned in the Schedule of Activities in the study protocol.

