8.2.3. Pharmacokinetic Analysis

The PK parameters detailed in [Section 6.3](#) will be listed and summarized for participants in the appropriate analysis sets (as defined in [Section 5.3](#)). Missing values will be handled as detailed in [Section 7](#).

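### Does the one-dose definition of the Evaluable set disable the rule for replacing participants when fewer than 4 are evaluable?

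*Protocol*

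**What the plan says.** Protocol 4.1 and SAP 2.1 give the reason for the sample size and the replacement rule in consecutive sentences of one paragraph. The SAP's version of the reason is that "6 participants will be enrolled to ensure evaluable data is acquired in at least 4 participants". Both documents then state: "Participants who withdraw from the study may be replaced if the number of evaluable participants is less than 4".

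Protocol 9.2 states the rule differently: "Participants who withdraw from the study, for non-safety reasons, may be replaced if the number of participants with evaluable data is less than 4". It counts participants with data rather than evaluable participants, and it adds a limit on the reason for withdrawal.

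Protocol 9.3 and SAP 5.1 define a set called Evaluable: "All participants assigned to study intervention and who take at least 1 dose of study intervention". The Safety set in the same sections has the same membership rule. The other sets are based on data. Extent of Excretion requires evaluable urinary and fecal radioactivity, and the PK Parameter set requires at least one parameter of interest. SAP 8.2.3 says that the PK parameters "will be listed and summarized for participants in the appropriate analysis sets", and points to the PK sets in SAP 5.3.

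The inputs to F and Fa are stated. F uses oral and IV dose-normalized AUC from Period 2 (Protocol 9.4.2.1.2, SAP 8.2.3.2). Fa uses percent of the radioactive dose in urine to 48 hours, oral in Period 1 and IV in Period 2 (Protocol 9.4.2.1.3.2, SAP 8.2.3.3.2).

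**The concern.** If the word evaluable in the replacement rule carries the meaning of the set with that name, a man who takes the Period 1 dose and leaves before Period 2 still counts. The count would stay at 6 however many men left, and the option to replace would never open, although the aim was usable data from at least 4.

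F and Fa are the estimates exposed. F needs both Period 2 profiles and a paired Fa needs urine from both periods. Either one above 0.85 leads to a high-permeability classification (Protocol 4.2 and 9.4.2.1.3.2), so the number of men behind them matters even though no hypothesis is tested.

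Two further points sharpen the worry. No section ties the F or Fa data to the minimum of 4. And if a man withdraws for a safety reason, Protocol 4.1 and SAP 2.1 would allow a replacement while Protocol 9.2 would not.

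**Working it through.** **The plan's own figure.** There is no calculation to reproduce. Protocol 9.2 takes 6 from industry practice and says that neither empirical data nor hypothesis-testing criteria lie behind it. No SD, precision target or dropout rate is given.

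**The trigger under each reading.** Suppose 6 men are dosed in Period 1 and *w* are lost before Period 2.

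| *w* | One-dose count | Below 4? | Men with Period 2 data (6 − *w*) | Below 4? |
|---|---|---|---|---|
| 0 | 6 | no | 6 | no |
| 1 | 6 | no | 5 | no |
| 2 | 6 | no | 4 | no |
| 3 | 6 | no | 3 | yes |
| 4 | 6 | no | 2 | yes |

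The two readings part at *w* = 3.

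**Which reading the text supports.** The enrolment sentence in Protocol 4.1 and SAP 2.1 speaks of data obtained, and the replacement sentence follows it directly. Protocol 9.2 also counts men with data. No replacement sentence cites the analysis set, which Protocol 9.3 introduces for analysis. Under the one-dose meaning, enrolling 6 to secure 4 would serve no purpose, because every dosed man would qualify at once. The data-based reading is the natural one.

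**How likely *w* ≥ 3 is.** Assume independent loss with probability *p* (not in the documents). P = Σ C(6,k) p^k (1−p)^(6−k) for k = 3 to 6: 0.2% at *p* = 5%, 1.6% at 10%, 9.9% at 20%.

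**What one man fewer costs F.** With complete pairs, the 90% log half-width is t(0.95, n−1)/√n × SD.
- n = 3: 2.920/1.732 = 1.686 × SD
- n = 4: 2.353/2 = 1.177 × SD
- Ratio: 1.686/1.177 = 1.43

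For an assumed SD of the log ratio of 0.1, 0.2 or 0.3, the interval multiplies and divides the estimate by 1.18, 1.40 or 1.66 at n = 3, against 1.12, 1.27 or 1.42 at n = 4.

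**What it costs Fa.** The mixed model keeps the Period 1 urine of men who leave. Without replacement there are 3 pairs plus 3 oral-only men; after one replacement, 4 pairs plus 3 oral-only. Set the total variance to 1 and the within-man correlation to ρ (assumed). The information on the two means is (number of pairs) × V⁻¹, with the number of oral-only men added to the oral diagonal.

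At ρ = 0.5, V⁻¹ has 4/3 on the diagonal and −2/3 off it. The variance of the oral-minus-IV difference is then 7/24 = 0.292 for 3 + 3, and 75/336 = 0.223 for 4 + 3. With Satterthwaite df of 2.71 and 3.83, the half-widths t(0.95, df) × √variance are 1.328 and 1.020, a ratio of 1.30.

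| ρ | 3 + 3 half-width | 4 + 3 half-width | Ratio |
|---|---|---|---|
| 0.3 | 1.433 | 1.141 | 1.26 |
| 0.5 | 1.328 | 1.020 | 1.30 |
| 0.8 | 0.970 | 0.703 | 1.38 |

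SAP 8.1 names Kenward-Roger, whose standard-error adjustment is not included here.

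**Whether the analysis still runs.** SAP 7.3 stops the model only if more than 50% of values are not calculated, and presents summary statistics with 3 or more evaluable measurements. If the three lost men are counted as not calculated, 3 of 6 is exactly 50%, so the model runs on 3.

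**The case for a change.** The best case for changing the text is that a stated minimum should have a working definition before dosing. Three sentences meant as one rule disagree on what is counted and on which withdrawals qualify. The defined term in the plan points to the wrong count, the edit is only wording, and a definition settled after losses are known could look post hoc. There is also a man none of the three sentences covers. Protocol 7.2.1 says "Participants who request to discontinue receipt of study intervention will remain in the study", so one who declines the Period 2 doses but stays gives no data for F or paired Fa and has not withdrawn.

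The mismatch stands, and so does the missing link between the F and Fa data and the count of 4. Nor does any rule say when a urine collection is complete enough for Fa. The consequences do not follow. The sentences all say that men may be replaced, so leaving a safety withdrawal unreplaced is consistent with all three, and a replacement allowed by Protocol 9.2 is also allowed by the other two. Whether a man has both Period 2 AUCs or both urine collections can be judged without looking at his F or Fa, so settling the count late need not bias the estimates. Judging whether a collection is complete is work of the kind SAP 5.8 already leaves to the pharmacokineticist.

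The man who stops dosing but stays raises another matter. Protocol 7.1 says "If study intervention is definitively discontinued, the participant will not remain in the study for further evaluation", which sits badly with 7.2.1. Those two sections need reconciling on their own account, as a question of follow-up status and not of the replacement count.

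**Conclusion.** No change to the plan follows. This is loose terminology that the sponsor and analysts will fill sensibly: the minimum of 4 refers to men with usable data, and the plan says which data F and Fa use. The primary excretion endpoint is protected by its own data-based set. Neither document assigns an analysis to the one-dose Evaluable set, so its overlap with Safety is harmless.

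Rewording would alter no planned estimate, model or interval. It would not guarantee 4 men either, because replacement stays optional, and a replacement would need both periods (about 600 nCi in total and 12 to 25 inpatient days). With no stated precision or power behind 6, there is no target that 3 men would miss and 4 would meet.

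The loss in the worst plausible case is real but confined to width: about 43% on the log scale for F, and 26% to 38% for Fa at correlations 0.3 to 0.8. It arises only if at least 3 of 6 confined men are lost and the sponsor adopts the literal reading. The SDs, correlations and loss rates are assumptions. A loss rate well above 20% would make the event less remote, but the choice to replace would still be the sponsor's. Aligning the three sentences at a convenient amendment would be tidy, and is not needed for the analysis to be sound.
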